R	Does the research involve an intervention ? 
 An “intervention” here is understood as a systematic controlled change of participant conditions, which could be psychological or physical. It can include but is not limited to changes in diet, activity, access to information, or use of certain products. If yes, please provide details: It is an online survey in which participants will be randomly allocated to one of two groups. Each group will read a different appeal to take up the influenza vaccination.		
S	Does the study involve any additional ethical considerations or risks to participants or the researcher that are not listed above? If yes, please provide details:		

* Please refer to the University webpages on [Prevent Duty](#)

SECTION 5: STUDY DESIGN, METHODOLOGY & ANALYSIS

5.1 Clearly state the research aim(s) of the project:

To include:

- a clear explanation and justification for the research question(s)/aim(s)

To explore whether a message aligned with the moral foundations that underlie a person's political ideology increase their willingness to take up the seasonal influenza vaccination.

5.2 What are the objective(s) for the project:

- Objectives are intermediate steps that will help you to meet your research aim(s)

The main objective is to compare how people with different political ideologies respond to an appeal to take up the seasonal influenza vaccination, when the appeal content is aligned (or unaligned) with the moral foundations underlying those political ideologies.

We also plan to describe the characteristics of people who have and have not already taken up the vaccination (e.g. age), and their intentions to take up related health behaviours: receiving a future COVID-19 vaccination and wearing a mask.

5.3 Study design and data collection methods:

To include:

- a clear description of the study design and data collection methods
- a suitable design should reflect the aim(s) of the study
- This may include ethnography/observations, interviews, focus groups, questionnaires, document analysis etc.
 - Ethnography/Observations**- what/who will be observed, by whom, for how long? What equipment (if any) will be used for recording etc.?
 - Interviews**- who is conducting the interviews, how, where and when- by telephone/in person/skype; will they be recorded- how? How long will they last? How will the interview guide be developed? etc.

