****Receiving informed consent:** Participants will read an information sheet and give their informed consent to take part in the study. The information sheet will include statements that "The views expressed in the survey are not the views of the researchers or the University, but are here to allow participants to express their own views. You may not agree with some of the statements and are free to express disagreements." Only participants who indicate meeting all the eligibility criteria and who consent to the survey will be allowed to advance.

****Demographics:** Participants will be asked their age in years (options: 50 to 99+ and prefer not to say), resident region of England (9 ONS regions: <https://www.ons.gov.uk/geography/regions>), gender identity (male, female, non-binary, other, and prefer not to say) and ethnicity (5 UK groups, and prefer not to say: <https://www.ethnicity-facts-figures.service.gov.uk/style-guide/ethnic-groups>).

****Political ideology:** Before completing a 10-item conservatism scale used in a similar study investigating the effect of messages on behaviour (Day et al 2014), participants will be reminded that "We are interested in your opinions on a variety of issues. The views expressed here are not the views of the researchers or the University, but are here to allow participants to express their own views. You are free to express agreements and disagreements. We appreciate your honest responses." The questionnaire includes two questions related to each of the five issues: one worded in conservative terms (e.g. The economic market will naturally correct itself), while the other liberal terms (e.g. The government must regulate the economy). Participants will be asked how much they disagree or agree with each statement on a seven point scale from 'strongly disagree' to 'strongly agree'. Then they will be asked to self-report their political orientation measured using a seven point scale, from very liberal to very conservative; this question will act as a face-validity check that should highly correlate with the conservatism scale.

****Vaccination against influenza in 20/21 season:** Next participants will be asked whether they received an influenza vaccination in the 20/21 season already (Yes or No).

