--Participants who say "yes", will then be asked approximately when they received the vaccination (DD/MM/YYYY), where they received the vaccination (GP, pharmacy, other) and if they went with anyone to get their vaccination (no, a friend, a family member, or someone else). Lastly, they will be asked to describe why they took up the vaccination this year in a free-text box.

--Participants who say "no", will then be randomly allocated to view one of two appeals to take up the influenza vaccination. As in Kidwell et al.'s (2013) study, one appeal aligns with a conservative ideology and the other aligns with a liberal ideology. After reading these appeals, participants will be asked about their agreement with several statements on a seven point scale; these statements are manipulation checks to verify that the appeals evoke the immediately intended foundations. Then participants will be asked whether they intend to take up the influenza vaccination this seasons on a seven point scale, from 'strongly disagree' to 'strongly agree', and then be asked to explain their answer in a free-text box.

**Spill-over behaviours: Next all participants (those who vaccinated already and those who did not) will be asked about their intentions to take up a future COVID-19 vaccination when one becomes available, and their intentions to wear a face mask in a store that does not require face masks using the same seven point scale, from 'strongly disagree' to 'strongly agree'.

**Closing: Participants who have not already vaccinated will see debriefing information that reminds them that the study should not be construed as medical advice, and that they should speak to a medical professional if they are uncertain if they should take up the influenza vaccine. Hyperlinks are provided for participants to learn more about the study this study is based on and to learn more about the UK's influenza vaccinations policies this year. We also provide them with the opportunity to tell us anything else they think is relevant to the survey in a free-text box, or write "I prefer not to say". We have found this free-text box to be useful in previous surveys to source alternative explanations for our findings.

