Two check analyses will be performed. The first check is a face-validity check of the conservatism scale; this analysis will look at the correlation between participants' average political ideology scores to the 10-items and their self-reported political ideology. We expect to find a significantly positive correlation. The second check of the appeals; this analysis will look at how participants responded to the manipulation check items. We expect to find that participants who viewed the conservative appeal to have higher responses to an average of the two conservative checks than participants who viewed the liberal appeal, and vice versa.

The exploratory analysis will describe the proportion of participants that have already vaccinated, and the political ideologies, age, gender, ethnicity and current resident region of England for all participants.

For the participants who have already vaccinated, we will chart how many vaccinated on each week, up to the week the survey is disseminated. We will also describe the proportion who take up the vaccination at different locations, and the proportion who did so with a friend or family member. The reasons participants give for vaccinating will be thematically analysed. Lastly, we will describe the proportion of these participants who express some intention to engage in the spill-over behaviours: taking up the COVID-19 vaccination when it becomes available and wearing a face-mask in a store that does not require it.

For the participants who have not already vaccinated, we will assess whether the participants' demographic characteristics are similar across the randomly allocated groups using t-tests (for age) and chi-square tests (for categorical variables). Then, for each group we will describe the proportion who express some intention to be vaccinated, not to be vaccinated, and who neither agree nor disagree with the intention item. The reasons participants give for their responses will be thematically analysed. Lastly, we will describe the proportion of participants who express some intention to engage in the spill-over behaviours: taking up the COVID-19 vaccination when one becomes available and wearing a face-mask in a store that does not require it.

SECTION 6: RECRUITMENT

6.1 State the total number of planned participants and the sampling strategy; provide justification for this:

To include:

- *The rationale behind the proposed size of the sample*

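### Does describing characteristics for all participants in section 5.4 fail the objective of describing the vaccinated and the unvaccinated?

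*Protocol*

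**What the plan says.** The second objective in Protocol section 5.2 is to "describe the characteristics of people who have and have not already taken up the vaccination (e.g. age), and their intentions" regarding COVID-19 vaccination and mask wearing.

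Section 5.3 gives the order of the survey. Demographics and the conservatism scale come first, then the question on vaccination this season. Those not yet vaccinated "will then be randomly allocated to view one of two appeals to take up the influenza vaccination", then answer the manipulation checks and the influenza intention item. Those already vaccinated see no appeal and answer questions on when, where, with whom and why. After that, "Next all participants (those who vaccinated already and those who did not) will be asked about their intentions" on the two spill-over behaviours.

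The exploratory part of section 5.4 has three blocks:

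- **Everyone:** the proportion already vaccinated, and "the political ideologies, age, gender, ethnicity and current resident region of England for all participants".
- **Vaccinated:** week, place, companion, reasons and spill-over intentions.
- **Unvaccinated:** a balance check, which asks whether "demographic characteristics are similar across the randomly allocated groups using t-tests (for age) and chi-square tests (for categorical variables"). A summary of influenza intention comes next, under the wording "for each group we will describe the proportion who express some intention to be vaccinated" (or not, or neither). Reasons follow, and the block ends with the sentence "we will describe the proportion of participants who express some intention to engage in the spill-over behaviours".

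**The concern.** Two things look wrong on a first reading.

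**Characteristics.** The objective concerns two groups, while the sentence that lists the characteristics names everyone. The block on the vaccinated lists no demographics or ideology. The block on the unvaccinated uses demographics only to compare the two appeal groups, and the tests it names (t-test for age, chi-square for categorical variables) do not cover the continuous ideology score. Age is the objective's own example. The background in section 3 says the vaccine is free from 65 and only later in the season from 50, so age may well differ by vaccination status. Ideology by status would also show whether the balance sought through recruitment by party survives among the unvaccinated, who alone enter the primary analysis.

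**Spill-over intentions.** The unvaccinated answer these items after reading an appeal, and the vaccinated read none. Section 5.4 reports a proportion for each without comment. The words giving results per appeal group are attached to influenza intention and are not repeated for the spill-over items.

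If both sentences were followed in the narrowest way, the secondary objective would be only half met, and a reader might take the two spill-over proportions as directly comparable.

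**Working it through.** **1. The plan's own figure.** Section 6.1 recruits 200 and expects that up to 50% may already be vaccinated: 200 × (1 − 0.50) = 100 unvaccinated. This agrees with the 100 stated there.

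**2. What a purely pooled table would hide.** Take 100 vaccinated and 100 unvaccinated, with assumed shares aged 65 or over:

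| Vaccinated | Unvaccinated | Pooled |
|---|---|---|
| 50% | 50% | (50 + 50)/200 = 50% |
| 70% | 30% | (70 + 30)/200 = 50% |
| 90% | 10% | (90 + 10)/200 = 50% |

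A pooled table alone could not answer the objective. The question is whether the plan commits the analyst to one.

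**3. The passages side by side.**

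- Section 5.2 states the split by vaccination status for characteristics and intentions together.
- Section 5.3 explains in its own bracket what all participants means: "Next all participants (those who vaccinated already and those who did not) will be asked about their intentions".
- Section 5.4 restricts the primary analysis to the unvaccinated. Against that, the phrase in the exploratory part says who is included, namely both groups. It does not say that they are merged.
- The same sentence of 5.4 reports the proportion already vaccinated, and the next two paragraphs take the vaccinated and the unvaccinated in turn.
- Every participant gives the demographics ("Participants will be asked their age in years (options: 50 to 99+ and prefer not to say), resident region of England", gender and ethnicity) and completes the ideology scale before the vaccination question. The split therefore needs no new data.

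Read together, these lead to a table with a column for each vaccination group.

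**4. Spill-over against the objective.** Section 5.2 asks for these intentions in people who have and have not vaccinated. Section 5.4 gives one proportion for each. No objective asks for them by appeal, and no test or contrast between the vaccinated and the unvaccinated is planned.

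**5. What a split by appeal would offer.** The 95% half-width is 1.96 × √(p(1 − p)/n) for one proportion and 1.96 × √(2p(1 − p)/n) for a difference between two groups of n. Take p = 0.5 and assume equal allocation, since the ratio is not stated:

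| Vaccinated share | Unvaccinated | Per appeal | Pooled | Per appeal | Difference |
|---|---|---|---|---|---|
| 50% | 100 | 50 | 1.96√(0.25/100) = 9.8 points | 1.96√(0.25/50) = 13.9 points | 1.96√(0.50/50) = 19.6 points |
| 30% (assumed) | 140 | 70 | 1.96√(0.25/140) = 8.3 points | 1.96√(0.25/70) = 11.7 points | 1.96√(0.50/70) = 16.6 points |

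Only a difference of roughly 17 to 20 points or more would stand out. Nor would the split give an unexposed value to set beside the vaccinated, because both groups of the unvaccinated read an appeal.

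**The case for a change.** The best case for acting is that 5.4 does specify this description and attaches it to everyone, whereas elsewhere the authors wrote a split by status when they wanted one. On that view the plan does more than leave out a detail: it names the wrong set of people. The balance check yields demographics of the unvaccinated as a by-product at most, and nothing in 5.4 lists age or ideology for the vaccinated. Putting it right would cost almost nothing, and a pilot meant to inform a larger study has reason to know who had already been vaccinated.

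Part of this stands. No sentence in 5.4 expressly says that characteristics will be shown by vaccination status, and it would be tidier if one did. But the wording does not forbid the split, and the objective that the paragraph serves requires it. The columns of an exploratory descriptive table are commonly settled in a statistical analysis plan, which was not available here.

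The argument about political balance carries less weight. With 100 recruited from each party, assumed uptake of 40% and 60% would leave 60 and 40 unvaccinated. Those uptakes have no source in the protocol. The planned description is of the ideology score, not of party, so no table would wrongly show an even party split. Section 6.1 already accepts that the split may be imperfect. The ideology score is a mean-centred predictor in the primary regression, so its distribution among the unvaccinated is available to the analyst.

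The order effect on the spill-over items is real. It is also plain from section 5.3, and it is not the only difference: the vaccinated answer their own questions, including free text on why they vaccinated, before reaching those items. The two groups are self-selected in any case, and 5.3 calls the study observational with a randomised sub-component. A sentence of caution belongs in the report. As for the missing words on appeal group, they can fairly be read as carrying through the paragraph.

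**Conclusion.** The concern does not call for a change. On characteristics, 5.4 is less explicit than 5.2, but the two do not conflict, and an analyst working from the whole protocol would describe both vaccination groups. On spill-over intentions, the plan delivers what the objective asks; reporting by appeal and noting that the items follow an appeal are optional choices for the report.

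The effect on the trial's main result is nil: the primary regression and the 200 recruited stay as they are. The conclusion rests on reading 5.4 together with 5.2 and 5.3. If an analyst published only a pooled table, the descriptive objective would be partly unmet, but the split could be produced at any time from the same data.

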8.4 Who will have access to the study data?

Include individuals internal and external to the University and what level of access they have to the data e.g. anonymised, pseudonymised, identifiable etc.

Please note you will need to hold a University approved data sharing/processing agreement with each third party (external to the University) with whom data is to be shared.

Only the researcher at the University of Warwick will have access to the anonymous data for analysis purposes.

8.5 During the project, will data be hosted on any external platforms or use new technology?

Yes No

e.g. Apps, online survey tools (qualtrics, Bristol online surveys etc.), recruitment tools (Prolific, SONA etc.), cloud hosting tools.

If yes, please provide details of the system(s) and how they operate: Qualtrics (an online survey platform) and Prolific Academic (an online participant recruitment tool). Both these systems are already used by researchers at the University of Warwick.

Have you contacted Information Security ([contact]) regarding whether these technologies will be required to go through the Information Assurance workbook approval process?

<https://warwick.ac.uk/services/idc/informationsecurity/faqs/purchasingissues/> Yes No

How and when will the data be deleted and who by?

The data on Qualtrics will be deleted by the [name] by 1 September 2021

8.6 Will any research activities be audio or video recorded? Yes No

This needs to be clear in the participant information leaflet and consent form.

If yes, please provide details of what will be recorded, how long it will be kept, how it will be stored securely and how it will be deleted:

8.7 Will data be shared with any organisation external to the University for processing? Yes No

e.g. external transcription services, external statistics support, archiving etc.

If yes, please provide details of the sharing arrangements: clarify whether the data shared will be identifiable, the external organisation to which it will be sent and what contracts/arrangements are in place to safeguard the data and ensure the data processors/controllers will comply with data protection requirements:

8.8 Please detail how, where, in what format and for how long the research data will be stored securely, including on back up storage.

e.g. hard/electronic copies, locked filing cabinets in researcher's office, encrypted files, password protected devices, Warwick servers. Please also consider consent forms here. These should be stored separately to research data.

The anonymous data will be stored in Qualtrics online until the date stated in 8.5, and in a password protected file on the University of Warwick's servers for a period of at least 10 years from the date of any publication which is based upon it.

8.9 For this project, will data be processed, (to include the collation, collecting, distributing, sharing, accessing, reviewing, amending, deletion) transferred or stored in any Countries outside UK?

Yes No

e.g. the use of transcribing service outside the UK , market research company, cloud hosting provider

If yes, please provide details of the country/countries and the collection/transfer/storage arrangements:

8.10 Describe compliance and proportionality measures in place to satisfy the requirements of the Data Protection Act 2018 and the GDPR.

e.g. how will you ensure: fairness and transparency to research participants, data quality, data minimisation (only collect data which is necessary for the purpose(s) of the study), purpose limitation (no further processing of the data for purposes incompatible to those for which it was collected), de-identification of the data as soon as possible, appropriate technical and organisational measures in place to avoid unauthorised access and accidental loss or damage to data etc. Please see the accompanying guidance note from the Information Data Compliance Team to help answer this question.

No personally identifiable information will be requested in the survey.

There is the potential for participants to reveal their identity in the free-text responses requesting other information (e.g. "Why do you intend to receive the influenza vaccination this season (2020/21)?"). If this occurs, any identifiable information will be redacted from the retained datafiles described in 8.8 using the symbols "*****" to depict where a redaction has occurred. For example, we would redact any names, identification numbers (e.g. telephone), location data, and an online identifier (email addresses, IP addresses).

8.11 Is it anticipated that there will be any future use of the data? Yes No

If yes, please provide details (if known at this stage). This should be clear in the Participant Information Leaflet and on the consent form if there is potential for future use of this data:

The findings gathered from the data may be used to inform a future study.

SECTION 9: DISSEMINATION

Please describe the dissemination arrangements for the study:

To include:

- *What will happen to the results at the end of the study?*
- *Will this study have any pathways to impact? ('Pathways to Impact' are activities designed to ensure any potential impact is realised, measured and evidenced.)*
- *How and where will the results be reported/published?*
- *Are there any plans to notify/debrief the participants of the outcome of the study, either by provision of the publication, or via a specifically designed newsletter, presentation etc.?*
- *If it is possible for the participant to specifically request results from the researcher when would this information be provided e.g. after the Final Study Report had been compiled or after the results had been published?*

We will publish the results of this study in a weblog such as the Applied Research Collaboration Newsletter and/or the London School of Economics Politics and Policy Blog. As no contact information will be taken from participants during the survey, it will not be possible to make them aware of the findings

SECTION 10: FURTHER INFORMATION (OPTIONAL)

Please provide any further details/information relevant to this application that may aid the ethical review process.

To include:

- *For complex studies with multiple work packages, collaborators or steering groups, applicants may wish to submit a protocol or supplementary documents in addition to this application form detailing the roles and responsibilities of each party.*
- *Projects that require further approvals e.g. HRA approval for research in the NHS may also wish to submit a protocol for review.*
- *Peer review*
- *Patient and public involvement*
- *Flow diagram*
- *Data management plan*

N/A

SECTION 11: SUPPORTING DOCUMENTS

BSREC will need to review **all** participant facing documents associated with this application.

There may be more than one type of each document for each study, i.e. multiple participant information leaflets if there are different participant groups, or work packages.

Please specify below, which documents have been submitted with this application (where applicable):

- Participant information leaflet(s)
- Consent form(s)
- Poster(s)/advertisement(s)
- Invitation email(s)
- Questionnaire(s)/Survey question(s)
- Interview schedule(s)/topic guide(s)
- Data Collection form
- Data flow map
- Data Management Plan
- Risk assessment
- Protocol (optional- needs to be consistent with the application)
- Other, please specify:

SECTION 12. SIGNATURES AND DECLARATIONS

